[18F]CTT1057 scan intra-reader variability will be assessed by Cohen's Kappa statistic.

To assess the intra-reader variability, each of the three readers will re-read the same 20 randomly selected cases (with evaluable PET/CT) but each case will be presented to each reader in a random order. The readers will not reference any previous read results nor discuss any of these cases at any time during the read process. Each reader will use the same method to read the randomly presented cases as they did in the previous reads. Intra-reader agreement will first be evaluated separately for each of the 3 readers using Cohen's kappa statistic ( $\kappa_2$ ) as described below:

**Step 1:** A 2 by 2 contingency table (e.g. Table 2-1) will be calculated to summarize the frequency of concordance and discordance for patient-level positivity or negativity. The counts in the table will add up to 20 in total (i.e. a + b + c + d = 20).

Table 2-1 Example 2 by 2 Contingency Table for Each Reader

		New Reads	
		Positive	Negative
Original Reads	Positive	a	ь
	Negative	С	d

**Step 2:** Based on the contingency tables described above, a simple agreement rate, i.e.  $\frac{a+d}{a+b+c+d}$  and its corresponding 95% confidence interval (Agresti A, Coull BA 1998) will be estimated based on normal approximation.

Step 3: Finally, a Cohen's kappa statistic ( $\kappa_2$ ) and its corresponding 95% confidence interval will be estimated (Cohen J 1960; Cohen J 1968; Fleiss J, Levin B, Paik MC 2003) using the formula  $\kappa_2 \pm 1.96SE$ , where  $SE = \sqrt{\frac{p_0(1-p_0)}{N(1-p_e)^2}}$  (McHugh M 2012). Let N denote the number of re-reads (N=20), k the number of categories (k=2),  $n_{i1}$  the number of times the original reads were assigned to i (i=1,...,k) and  $n_{i2}$ the number of times the re-read were assigned to i (i=1,...,k). Then Cohen's kappa can be calculated as  $\kappa = \frac{p_0-p_e}{1-p_e}$ , where  $p_0$  is the relative agreements among the original and re-reads ( $p_0 = \frac{a+d}{a+b+c+d}$  in Table 2-1) and  $p_e = \sum_{i=1}^k \frac{n_{i1}}{N} \frac{n_{i2}}{N}$  ( $p_e = \frac{a+b}{N} \frac{a+c}{N} + \frac{c+d}{N} \frac{b+d}{N}$  in Table 2-1). Intra-reader variability will be calculated for the F-SAF.

For region-level diagnostic performance parameters:

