# 3.1 Primary endpoints(s)

This study is planned to recruit approximately 190 participants. The sample size calculation is based on the co-primary endpoints of region-level CLR and the patient-level PPV of [18F]CTT1057.

The assumptions for sample size calculations are based on the estimates from data available from prior studies.

The primary endpoint is to evaluate region-level CLR (prostate region, PLN, extra-pelvic lymph nodes, skeletal, and visceral) and patient-level PPV of [F]CTT1057 PET for detection of tumor location confirmed by CTS. Based on the results of previous studies, the following distribution of disease across regions are anticipated: Prostate bed: 30%, pelvis: 15%; extrapelvic soft tissue: 20%; bone metastases: 35% (Eiber et al 2015, Ceci et al 2015, Van Leeuwen et al 2016). It is anticipated that the CLR for the five regions and for all regions combined using conventional imaging ranges from 30-60%. An overall CLR for [F]CTT1057 PET of at most 50% will be considered as unacceptably low. Hence, the null hypothesis that the CLR is at most 50% will be tested against the alternative hypothesis that the CLR is greater than 50%.

The BCR population targeted in this study is expected to have similar PSA values as prior studies (Morris et al 2020) of approved diagnostic PET agents for PCa such as [F]-fluciclovine, which had a 27% PPV for patients with PSA values that were less than 1.78, as noted in their summary basis of approval. Thus, a patient-level PPV of 20% will be considered as unacceptably low. The [F]CTT1057 positive patient rate (detection rate) for the study population is 80% based on [F]-fluciclovine studies. The sample size calculation will be performed based on the null and alternative hypotheses as follows.

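### The intra-reader kappa interval in SAP 2.6.2 has zero width when a reader repeats all 20 calls, and its coverage falls well below 95% if true kappa is about 0.8 or higher

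*SAP*

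**What the plan says.** SAP 2.6.2 describes the intra-reader analysis in three steps, done separately for each of the three central readers.

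- **Data.** In the SAP's words, "each of the three readers will re-read the same 20 randomly selected cases (with evaluable PET/CT"). Step 1 cross-tabulates original against new patient-level calls: "The counts in the table will add up to 20 in total".
- **Step 2.** The simple agreement rate (a+d)/20 is reported "and its corresponding 95% confidence interval (Agresti A, Coull BA 1998) will be estimated based on normal approximation".
- **Step 3.** Cohen's kappa is reported with kappa ± 1.96 SE, where SE = sqrt(p0(1−p0)/(N(1−pe)²)). The inputs are fixed: "Let N denote the number of re-reads (N=20), k the number of categories (k=2").

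The section has no rule for p0 = 1, for pe = 1 (every case given the same call on both reads, so kappa is undefined) or for limits above 1. Neither document states an expected kappa, a target precision or a reason for choosing 20 re-reads.

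The only planning value for how many scans are positive is in SAP 3.1: "positive patient rate (detection rate) for the study population is 80% based on" fluciclovine studies. Under the success rule in SAP 2.5.2, study positivity depends only on the two co-primary thresholds.

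**The concern.** The SE contains the factor p0(1−p0), so it is zero whenever observed agreement is perfect. Perfect agreement is a realistic result when one reader repeats a yes/no call on 20 scans. The table would then show kappa 1.00 with a 95% interval of 1.00 to 1.00, which claims certainty from 20 cases, about 4 of them expected to be negative.

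Protocol 4.1 gives reader variability a real purpose: to show that interpretation is consistent enough for reliable diagnosis. The interval is weakest at high agreement, which is the result most likely to be cited as evidence of consistency. What is at stake is the honesty of the error bars on a named secondary endpoint, not the trial's success decision.

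**Working it through.** **Inputs.** From SAP 2.6.2: N = 20, two categories, and the interval formula above. From SAP 3.1: 80% positive, applied here to the re-read cases as an assumption, with 50% and 90% as a range. True kappa is not in the documents, so 0.4 to 0.9 is an assumed range. The plan states no coverage or precision for this endpoint, so there is no figure of its own to reproduce.

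**Step 1: the formula at perfect agreement.** Take 16 cases positive on both reads and 4 negative on both. Then p0 = 1, pe = 0.8×0.8 + 0.2×0.2 = 0.68, kappa = 1 and SE = sqrt(1×0/(20×0.32²)) = 0. The interval is 1.00 to 1.00.

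**Step 2: the formula with one discordant read.** Take a=15, b=1, c=0, d=4. Then p0 = 0.95, pe = 0.80×0.75 + 0.20×0.25 = 0.65 and kappa = 0.30/0.35 = 0.857. SE = sqrt(0.95×0.05/20)/0.35 = 0.139, so the interval is 0.584 to 1.130.

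**Step 3: exact coverage.** I enumerated all 2×2 tables of 20 under a multinomial with equal margins. With positive rate π and true kappa κ, each discordant cell has probability q = π(1−π)(1−κ), and the concordant cells have π−q and 1−π−q. For π = 0.8 and κ = 0.8, q = 0.032. The probability of 20/20 agreement with both calls present is (1−0.064)^20 − 0.768^20 − 0.168^20 = 0.266 − 0.005 − 0.000 = 0.261.

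At 80% positive (coverage, misses and upper limits computed where kappa is defined):

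| True kappa | Coverage | P(interval is 1.00 to 1.00) | Misses due to zero width | P(upper limit > 1) |
|---|---|---|---|---|
| 0.4 | 94.3% | 1% | 1.3 of 5.7 points | 43% |
| 0.6 | 90.3% | 6% | 6.3 of 9.7 points | 69% |
| 0.7 | 86.4% | 13% | 13.0 of 13.6 points | 75% |
| 0.8 | 73.5% | 26% | 26.3 of 26.5 points | 70% |
| 0.9 | 48.1% | 51% | 51.8 of 51.9 points | 48% |

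From kappa 0.7 upward the shortfall is almost entirely the zero-width intervals.

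**Step 4: other positive rates.** For true kappa 0.4, 0.6, 0.7, 0.8 and 0.9, coverage at 50% positive is 94.6%, 91.9%, 86.6%, 87.2% and 63.9%. At 90% positive it is 91.2%, 81.7%, 71.8%, 56.5% and 33.8%. Kappa is undefined in under 1% of samples at 80% positive, and in about 4% to 10% at 90% positive over this kappa range.

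**Step 5: alternatives on the same 20 reads.** The goodness-of-fit interval keeps the values of κ for which a three-cell chi-square (both positive, discordant, both negative) is at most 3.84. For the 16/4 perfect table that chi-square is [3.2(1−κ)]²/(12.8+3.2κ) + [3.2(1−κ)]²/(0.8+3.2κ) + 6.4(1−κ). At κ = 0.55 it is 0.14 + 0.81 + 2.88 = 3.83, so the interval is 0.55 to 1.00. Its coverage at 80% positive is about 92% to 95%. A profile-likelihood interval gives 0.72 to 1.00 for the same table, with coverage of 91% to 97% for kappa 0.4 to 0.9.

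**Step 6: is the simplified SE to blame?** No. The full large-sample SE at N = 20 and 80% positive gives simulated coverage of 84%, 71% and 47% at kappa 0.6, 0.8 and 0.9.

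**The case against.** The strongest reply is that the consequence is small and the reader of the report is not left blind. Intra-reader agreement is a secondary endpoint with no hypothesis, threshold or pass mark, and no other efficacy result uses kappa. Step 1 prints the 2×2 counts. Step 2 puts beside kappa an agreement rate with an interval citing Agresti-Coull, which does not collapse: at 20/20 its lower limit is about 0.81, against 0.83 for the exact interval. The kappa formula is a published large-sample one. All of this stands. It limits the importance of the point but does not repair the kappa interval. It also removes any need to replace the Step 2 method, although the phrase about normal approximation could be read as plain Wald, which would also collapse.

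A reader might infer several stronger things that the documents do not support.

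- **That coverage is far below 95% in general.** It depends on true kappa, which the documents do not give. At kappa 0.4 to 0.6 and 80% positive, coverage is 94% to 90%.
- **That limits above 1 cause the undercoverage.** Kappa cannot exceed 1, so cutting the interval at 1 leaves coverage unchanged.
- **That a collapse for at least one reader is close to a three-in-four event.** At 95% agreement, 1 − (1 − 0.95^20)³ = 74% for perfect agreement by at least one reader, but this treats the readers as independent. They re-read the same 20 cases, and shared hard cases can correlate their disagreements.
- **That only one replacement is right.** The two alternatives give lower limits of 0.55 and 0.72 for the same table, so the choice between them is a matter of judgement.

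**Conclusion.** The point holds in conditional form. Followed as written, Step 3 gives a zero-width 95% interval whenever a reader repeats all 20 calls with both categories present. At 80% positive this happens in 26% of samples if true kappa is 0.8 and in 51% if it is 0.9, and coverage is then 73% and 48%. At kappa 0.4 to 0.6 the interval performs acceptably to modestly low. Limits above 1 occur in 43% to 75% of samples over kappa 0.4 to 0.9 and are a presentation fault only.

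These figures rest on the assumed kappa range, on carrying the 80% planning rate over to the re-read cases, and on equal margins for the two reads. The zero-width result at perfect agreement needs none of these assumptions. The change is worth making before the analysis is run, but it has no bearing on the co-primary conclusions.

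**What to change.** In SAP 2.6.2:

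- **Step 3.** Replace kappa ± 1.96 SE with a named interval that is valid at p0 = 1 and stays within range. The Donner-Eliasziw goodness-of-fit interval for a binary kappa is one choice and a profile-likelihood interval is another. Name one of them in advance.
- **Step 3.** Add that kappa is reported as not estimable when pe = 1, with the 2×2 counts shown.
- **Step 2.** Keep the cited Agresti-Coull interval. State that it is not the plain Wald interval, and cut it at 1 for display, since its upper limit at 20/20 exceeds 1.

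The cost is a few sentences and a short program. The intervals will be visibly wider at high agreement, which reflects what 20 cases can show. No extra reads or data are needed. Keeping the present formula and adding reads would be a slower remedy: at kappa 0.8 and 80% positive, simulated coverage is 89% with 50 re-reads and 93% with 100.

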#### • Region-level sensitivity

- Region-level specificity
- Region-level negative predictive value
- Region-level accuracy

Number of TP, TN, FP, FN regions will be presented and used to calculate the diagnostic performance parameters.

Two-sided 95% CI's for (overall) region-level diagnostic performance parameters will be calculated using a logistic random-effects models taking into account the correlation among regions within a participant.

For different regions (i.e. prostate region, PLN, skeletal, extra-pelvic lymph nodes and visceral), two-sided exact binomial 95% CI's for region-level diagnostic performance parameters will be calculated.

Concordance between [ $^{18}$ F]CTT1057 and [ $^{68}$ Ga]Ga-PSMA-11 For detection of PSMA-positive lesions, positive percent agreement (PPA) will be calculated to assess the concordance. Logistic random-effects models will be used taking into account the correlation among lesions within a participant overall and by region. When calculating PPA, the number of positive lesions identified and anatomically co-localized by both [ $^{18}$ F]CTT1057 and [ $^{68}$ Ga]Ga-PSMA-11 for participant i (see  $\frac{1}{18}$ ),  $y_i$ , follows the binomial distribution with parameter ( $n_i$ ,  $p_i$ ),

$$y_i|b_i\sim \text{Binomial}(n_i,p_i)$$

pi denotes the PPA for participant i, ni corresponds to the denominator in the PPA definition, i.e. the number of all positive lesions identified by [Ga]Ga-PSMA-11 for participant i.

PPA along with two-sided 95% CIs will be estimated by the logistic regression model with random effects below:

$$\log\left(\frac{p_i}{1-p_i}\right) = \mu + b_i$$

where  $p_i$  is the lesion-level PPA for participant i,  $\mu$  is the fixed effect of overall mean,  $b_i$  is the random effect of participants (clusters).  $b_i$  follows a normal distribution :  $b_i \sim N(0, \sigma_h^2)$ .

The same analysis will be repeated by region and combining skeletal, extra-pelvic lymph nodes, and visceral regions (M1).

The number of PSMA-positive lesions identified on [F]CTT1057 PET/CT, on [Ga]Ga-PSMA-11 PET/CT, on [F]CTT1057 PET/CT but not on [Ga]Ga-PSMA-11, on [Ga]Ga-PSMA-11 but not on [F]CTT1057 PET/CT, and the number of PSMA-positive lesions identified on both[F]CTT1057 and [Ga]Ga-PSMA-11 PET/CT will be displayed overall, by region and by combined M1 region.

The above analyses will be provided by each central reader using the F-SAF.

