All patients will undergo 2 PET/CT scans: a [¹⁸F]CTT1057 PET/CT scan (investigational imaging agent) and a [⁶⁸Ga]Ga-PSMA-11 PET/CT scan (as part of the CTS level 2 if required, and for the secondary endpoint of assessment of concordance between [¹⁸F]CTT1057 and [⁶⁸Ga]Ga-PSMA-11 for detection of lesions) (see Section 3). The two scans will be performed at least 2 weeks apart for each participant in order to ensure a clean safety profile assessment for each PET imaging radiopharmaceutical. Moreover, in order to counter-balance any potential change in lesions between the 2 PET/CT scans, the PET/CT scan sequence for each patient will be assigned at random, in a 1:1 ratio after enrolment (see Section 6.1.4 for the definition of PET/CT scan sequence).

There is preliminary evidence that PSMA PET imaging allows detection and localization of metastases in some BCR patients leading to significant changes in therapeutic approaches (Afshar-Oromieh et al 2017). Therefore, assessment of the clinical impact of [¹⁸F]CTT1057 PET/CT in patient management by means of 2 questionnaires has been included as a secondary endpoint. Further details on the questionnaire are provided in Section 3. In order to reproduce as much as possible the real clinical context, the treating physician / Clinical Study Investigator will receive the [¹⁸F]CTT1057 PET/CT scan report from a local nuclear medicine physician who will be blinded to the results of the [⁶⁸Ga]Ga-PSMA-11 PET/CT scan, but will not be blinded to other patient data.

In addition, the imaging diagnostic procedures included in CTS Level 2 will be read by local nuclear medicine physician or radiologist with expertise in reading oncology PET/CT scans as per SoC, who will be blinded to the [18F]CTT1057 PET/CT scan results, but not to other patient data.

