#### 2.2 Analysis sets

The Full Analysis Set (FAS) includes all randomized participants.

The Efficacy Analysis Set (EFF) includes all randomized participants who receive the dose of investigational treatment (i.e. [18F]CTT1057), have both an evaluable [18F]CTT1057 PET/CT scan imaging and at least one evaluable CTS assessment, and have not received any prohibited systemic antineoplastic therapy before the completion of PET/CTs and CTS procedures.

The [18F]CTT1057 Safety Set (F-SAF) includes all participants who received the investigational treatment (i.e. [18F]CTT1057).

The [68Ga]Ga-PSMA-11 Safety Set (Ga-SAF) includes all participants who received [68Ga]Ga-PSMA-11. Participants will be analyzed according to the study treatment received.

The **Safety Set (SAF)** includes all participants who received at least one of [F]CTT1057 or [Ga]Ga-PSMA-11.

The number (%) of participants in each analysis set will be summarized and information about analysis sets for each participant will be displayed in a listing.

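### The lesion-level concordance counts in SAP 2.6.2 use the F-SAF, which does not require a [68Ga]Ga-PSMA-11 scan, so the [18F]CTT1057-only count can include lesions with no gallium image; PPA is unaffected (minor)

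*SAP*

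**What the plan says.** Concordance between the two tracers is a secondary endpoint. SAP Table 1-1 defines it in terms of both the location and the number of PSMA-positive lesions. SAP 2.6.2 provides two outputs.

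- **PPA**, from a logistic model with a random participant effect. Its denominator is "the number of all positive lesions identified by [ 68 Ga]Ga-PSMA-11 for participant i". The only fixed term is the intercept, which "is the fixed effect of overall mean".
- **Lesion counts**: on [18F]CTT1057, on gallium, on the first but not the second, on the second but not the first, and on both. These "will be displayed overall, by region and by combined M1 region".

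For the analysis set, SAP 2.6.2 states: "The above analyses will be provided by each central reader using the F-SAF". Under SAP 2.2 the F-SAF "includes all participants who received the investigational treatment", meaning [18F]CTT1057. It sets no condition on a gallium dose, scan or evaluable image.

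SAP 2.6.3 excludes from the secondary efficacy analyses only participants dosed with [18F]CTT1057 who did not complete that scan. SAP 2.6.4 says that missing data are not imputed. Protocol Section 3 and Table 8-2 make the gallium scan mandatory for everyone randomised. Protocol 9.1.1 nevertheless defines treatment discontinuation as one of the two injections not being given, and Protocol 6.1.5 allows a participant to stop after the first agent.

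Protocol 4.1 explains that scan order was randomised 1:1 "in order to counter-balance any potential change in lesions between the 2 PET/CT scans".

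**The concern.** A table that compares two tracers lesion by lesion is a paired table: each lesion needs an image from both. The F-SAF guarantees only one of the pair. A Sequence 1 participant who leaves after the first scan has [18F]CTT1057 lesions and no gallium image, yet belongs to the stated analysis set.

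The cell at risk is the one a reader would take as evidence that the investigational tracer finds lesions the comparator misses. Any lesion placed there for want of a gallium image errs in favour of [18F]CTT1057. Protocol 4.1 gives a reason for randomising the scan order, but the concordance output has no display by sequence, so a reader could see neither an order effect nor a difference in completeness between the two orders.

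**Working it through.** The documents give no expected value, power or sample size for concordance, so there is no plan figure to reproduce. Three checks were made.

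**1. Effect on PPA.** A participant with no gallium scan has n_i = 0 and y_i = 0. The binomial term is p^0 × (1 − p)^0 = 1 for every p, so the participant adds nothing to the likelihood. A numerical check fitted the SAP's random-intercept model by maximum likelihood to one simulated data set of 152 participants (280 gallium-positive lesions, 212 of them also on [18F]CTT1057). Adding 0, 5, 10 or 19 participants without a gallium scan gave PPA 0.7876 each time, with the same log-likelihood. The value 0.7876 means nothing in itself; what matters is that it does not move.

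**2. Effect on the counts.** The table implies that

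total on [18F]CTT1057 = on both + on [18F]CTT1057 only.

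For a participant with no gallium scan, the count on both is 0. If that participant's lesions enter the total, as the stated set implies, they must also enter the [18F]CTT1057-only count or the cells do not add up. The gallium total, the gallium-only count and the count on both are unchanged.

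**3. Size.** Inputs:

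- Planned enrolment of 190 at 1:1 (SAP 1.1), so about 190 / 2 = 95 in Sequence 1.
- Share d of Sequence 1 lost before the gallium scan: 5%, 10% or 20% (assumed).
- [18F]CTT1057-positive lesions per participant: 1 to 3 (assumed).
- True [18F]CTT1057-only share s among [18F]CTT1057-positive lesions: 10% or 20% (assumed).

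Participants without a gallium scan: k = 95d, which is 4.75, 9.5 and 19, taken as 5, 10 and 19. Added lesions: k × 1 to k × 3. With equal lesions per participant and all 190 contributing, the share shown is [s(190 − k) + k] / 190.

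| d | k | Added lesions | Shown if s = 10% | Shown if s = 20% |
|---|---|---|---|---|
| 5% | 5 | 5–15 | (18.5 + 5)/190 = 12.4% | (37 + 5)/190 = 22.1% |
| 10% | 10 | 10–30 | (18 + 10)/190 = 14.7% | (36 + 10)/190 = 24.2% |
| 20% | 19 | 19–57 | (17.1 + 19)/190 = 19.0% | (34.2 + 19)/190 = 28.0% |

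Only Sequence 1 is used because Sequence 2 participants are due their gallium scan first, so few should reach [18F]CTT1057 without one.

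**The case against.** Four points can be made for the plan.

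**PPA is the named concordance measure and is sound.** This stands in full. A reader might infer from the choice of set that the concordance estimate itself is biased. It is not, because the denominator shuts these participants out.

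**The SAP never says that a lesion without a gallium image counts as gallium-negative, and its no-imputation rule points the other way.** This stands in part. The SAP is silent on how such a lesion is classified, so it cannot be said that the plan instructs all of them to be scored as [18F]CTT1057-only. But the rule does not close the gap: the [18F]CTT1057 lesions are observed data from members of the stated set, and counting them needs no imputation. The programmer is left to choose.

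**Part of the concordance instructions may not be visible.** The definition of y_i carries an unreadable cross-reference, and the SAP document history cites a Section 5.5 that is not in the public text. This is why the point is limited to the absence of a visible rule.

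**Sequence is used, and 1:1 allocation balances order without a model term.** This stands. A reader might infer that the randomised order is never used. In fact it appears in the assessment windows (SAP 2.1.1), disposition (2.3.1), attribution of treatment-emergent events (2.7.1), deaths (2.7.2) and the vital signs listing (2.7.4.2), and the time between scans is summarised (2.4.1). What is missing is only a concordance display by sequence. A sequence fixed effect in the PPA model is not needed.

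**Conclusion.** The point holds for the lesion counts only. Run in the F-SAF as written, the total [18F]CTT1057 count and the [18F]CTT1057-only count can include lesions from participants who were never imaged with gallium, and the error runs in favour of the investigational tracer. Over the assumed range this is about 5 to 57 lesions, moving a true [18F]CTT1057-only share of 10% to between about 12% and 19%, or of 20% to between about 22% and 28%. The lower end is more plausible, since the gallium scan is mandatory. If nobody lacks a gallium scan, the effect is nil.

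The 20% loss is a bound for the illustration. A reader might take the plan's 20% dropout allowance as an expected rate of missing gallium scans, but SAP Section 3 uses it for evaluability on the co-primary endpoints and gives no rate for gallium scans.

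Severity is minor: the endpoint has no test, no threshold and no role in study success.

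**What to change.** In SAP 2.6.2, replace the F-SAF for concordance with the participants who have both an evaluable [18F]CTT1057 and an evaluable [68Ga]Ga-PSMA-11 PET/CT scan, for both PPA and the count tables. Report the number of F-SAF participants this excludes, by randomised sequence. Show PPA and the counts descriptively by sequence as well as overall.

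Moving to the EFF would not solve the problem, because that set needs only one evaluable CTS assessment, which need not be the gallium scan.

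The cost is a wording change, one derived flag and an extra table split. It needs no new data, and PPA is unchanged by dropping participants without a gallium scan.
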